The objective of this randomized, triple-blind, placebo-controlled, parallel study is to investigate two products, UP360 and UP446, compared to a placebo on supporting immune function in a healthy adult population. The increase in lymphocyte populations and Ig production with supplementation of the IPs compared to placebo will be compared in the 28-day pre- and post-vaccination periods to examine the immune boosting effects of the products. Other quantitative markers of immune function will be measured including erythrocyte sedimentation rate (ESR), C-reactive protein (CRP) and complement C3 and C4 proteins. To support the alterations in immunity, the Wisconsin Upper Respiratory Symptom Survey (WURSS)-24 will be used as a subjective measure of signs and symptoms of URTI, inclusive of cold, flu and COVID-19. The impact of COVID-19 on wellbeing and quality of life will also be assessed to examine the potential confounder of the pandemic on immune function. The findings of this study will provide evidence for UP360 and UP446 to support immune function with flu vaccination, understand external factors that influence immunity during the cold and flu season and COVID-19 pandemic and potentially inform public health policy regarding community spread influenza and COVID-19.

Participants will be healthy men and women who have not been vaccinated with the quadrivalent influenza vaccine (QIV) but are willing to receive it during this study. Participants will be between the ages of 40 to 80 years old to include older adults that are the target of national vaccination programmes and those potentially most likely to have reductions in COVID-19 mortality with influenza vaccination. Participants'

Protocol 21UIHU A randomized, triple-blind, placebo-controlled, parallel clinical trial to investigate two products on supporting immune function in healthy adults

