medical history, lifestyle factors and laboratory results will be reviewed to assess eligibility and may be excluded if there is any condition or lifestyle factor that the QI determines may affect study measures or safety of the participant. To avoid interactions with the active ingredients in the IPs, participants on medications will be assessed on a case-by-case basis to ensure their eligibility and safety with special reference to the medications listed in the Investigational Brochure. All participants will be asked to maintain their current diet, medication, supplements, exercise and sleep while avoiding taking any new supplements during the study to avoid confounders. Information regarding occupation, social interactions, history of flu vaccination, URTIs, allergies, and lifestyle factors will be collected to account for inter-individual variability on study outcomes. The inclusions and exclusions in this study will ensure only participants who are healthy, stable, and have no comorbidities are enrolled.

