#### **Primary outcome:**

The difference between UP360, UP446 and placebo in the increase in immune parameters as assessed by lymphocyte populations (CD3+, CD4+, CD8+, CD45+, TCRγδ+, CD3-CD16+56+) and immunoglobulins (IgG, IgM, and IgA) in blood from baseline at Day 28 and 56

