#### Assessments include:

- 1. Return and review study diaries and modified WURSS-24 Questionnaires
- 2. Return unused investigational product in the original packaging and remnants and calculate compliance by counting the returned unused investigational product
- 3. Review concomitant therapies and adverse events
- 4. Seated BP and HR measurements
- 5. Collection of blood samples for the analysis of:
  - a. CBC, electrolytes (Na, K, Cl), glucose, eGFR, creatinine, AST, ALT, ALP, and total bilirubin
  - b. ESR, CRP, complement C3, complement C4, IgG, IgM, IgA, CD3+, CD8+, CD4+, CD45+, TCR $\gamma\delta$ +, CD3-CD16+CD56+
  - c. Cytokines, HMGB1, NF-κB, Nrf-2, 8-iso-prostaglandin F2α, CAT, GSH-Px, SOD, MDA, AGEs, HI titers for specific strains of virus for future analysis
- 6. Administer Vitality Questionnaire (Section 9.9.4)
- 7. Administer COVID-19 QoL (Section 9.9.5)
- 8. Administer flu vaccine (QIV)
- 9. Dispense new IP
- 10. Dispense new study diaries
- 11. Dispense new modified WURSS-24 Questionnaires (Section 9.9.3)

The next appointment will be scheduled for Day  $56 \pm 2$  days.

Participants will be reminded to follow all instructions provided prior to their next appointment.

## 9.7 Processing Participants who get COVID-19 or Flu After Vaccination and Prior to Day 56

The WURSS-24 Questionnaires and daily diaries will be reviewed by clinic staff. Clinic staff will identify those participants that self-report they have COVID-19 or flu. Regarding flu, participants will be queried on if they have a diagnosis from their PCP. In the absence of such a diagnosis, based on indicated symptoms, participants will be assessed on a case-by-case basis by the QI.

Participants with self-reported diagnosis COVID-19 will be removed from the study. A COVID-19 diagnosis will be considered an AE and AE follow-up procedures will be followed.

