# 11.3 Statistical Analysis Plan

All the primary and secondary endpoints will be analyzed as continuous variables.

For each primary and secondary endpoint, descriptive statistics including number of subjects, arithmetic mean, standard deviation, median, minimum and maximum values will be presented for each study day and for the changes from baseline (Day 0) to each subsequent study day.

Changes in continuous endpoints from baseline will be calculated as:

Change to 
$$V_i = Value$$
 at  $V_i - Value$  at  $V_{baseline}$ 

Differences in changes between groups will be assessed by repeated measures mixed model ANOVA, with study group and visit as the fixed effects. Each model will include the baseline value as a covariate. Within group changes will be assessed by the paired t-test or Wilcoxon Sign Rank test, depending on the distribution of the data. All tests of significance for primary outcomes will be performed at one-sided, and for secondary outcomes will be performed at two-sided, alpha level = 0.05 unless otherwise specified.

The co-primary outcomes will be interpreted individually and together as a real-life global assessment of immune function. As such, there will be no adjustment for multiple outcomes (38-42). This is in accordance with the following principles of the American Statistical Association's statement on statistical significance

and p-values: #3 – "scientific conclusions and business or policy decisions should not be based only on whether a p-value passes a specific threshold;" #4 – "proper inference requires full reporting and transparency;" and #6 – "by itself, a p-value does not provide a good measure of evidence regarding a model or hypothesis" (43).

Missing data for the primary and secondary endpoints will be imputed with last-observation-carried-forward (LOCF) method or multiple imputation as a sensitivity analysis for ITT Population. No imputation will be performed for PP and Safety Population.

Probabilities  $\leq 0.05$  will be considered statistically significant. All statistical analysis will be completed using the R Statistical Software Package Version 3.6.3 or newer for Microsoft Windows (44).

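### The between-group model in Section 11.3 names no group-by-visit term, so fitted as written it averages the Day 28 and Day 56 differences that the primary outcome keeps separate

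*Protocol*

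**What the plan says.** The primary outcome in Section 5 of the protocol is "The difference between UP360, UP446 and placebo in the increase in immune parameters as assessed by lymphocyte populations", together with immunoglobulins, measured "in blood from baseline at Day 28 and 56". Both visits are part of the definition.

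The Introduction (Section 4) says that the increase on each product relative to placebo "will be compared in the 28-day pre- and post-vaccination periods to examine the immune boosting effects of the products".

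Section 9.6 orders the Day 28 visit so that blood collection is item 5 and vaccination is item 8. The Day 28 sample is therefore taken before the vaccine and the Day 56 sample after it.

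Section 11.3 gives one between-group analysis: "Differences in changes between groups will be assessed by repeated measures mixed model ANOVA, with study group and visit as the fixed effects". It adds: "Each model will include the baseline value as a covariate". Results by visit are otherwise promised as descriptive statistics, and change within each arm is tested by a paired t-test or a signed rank test. Neither compares the arms.

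**The concern.** A model with study group, visit and baseline has one coefficient per product for the comparison with placebo, and that coefficient applies to both visits. The primary outcome asks for two differences per product.

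In many trials this would matter little, because two follow-up visits measure the same thing. Here the immune challenge falls between them. Day 28 reflects the product alone; Day 56 reflects the product plus the vaccine. That the product effect is equal before and after vaccination is something a vaccine model should examine, not assume.

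Three distortions are possible. An effect on the vaccine response alone is diluted. An effect before vaccination alone is reported at half size, as though it were present at both visits. Effects in opposite directions cancel. If the choice between averaged and by-visit tests stays unwritten, it could also be made after the data are seen.

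**Working it through.** **Inputs from the protocol.** Two post-baseline visits, Day 28 and Day 56 (Section 5). Fixed effects group and visit, plus baseline (Section 11.3). One-sided 5% tests for primary outcomes (Section 11.3). 25 randomised per arm with 20% loss, so 25 × 0.8 = 20 evaluable per arm (Section 11.1).

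**Inputs not in the protocol.** Section 11.1 gives no SD, ties its 80% power to no visit, and gives no between-visit correlation. Its detectable differences therefore cannot be reproduced. I assume a common SD s at both visits, a correlation rho of 0, 0.5 or 0.8 between a participant's two baseline-adjusted values, and a benchmark difference d that a Day 56 contrast would detect with 80% power.

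**Step 1: what the model estimates.** Let D28 and D56 be the true product-placebo differences. With complete data at both visits and n per arm:

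- main-effects model: estimate (D28 + D56)/2, variance s²(1 + rho)/n;
- model with group-by-visit: estimates D28 and D56 separately, each with variance 2s²/n.

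| True D28 | True D56 | Main-effects estimate |
|---|---|---|
| 0 | d | 0.5d |
| d/2 | d | 0.75d |
| d | d | d |
| d | −d | 0 |

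This step needs no assumed SD or correlation.

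**Step 2: simulation check.** Both models were fitted to 200 simulated trials with 20 per arm, correlation 0.5, and true effects of 0 at Day 28 and 1 at Day 56. The main-effects estimate averaged 0.45. The interaction model gave −0.06 and 0.96. The average of those two is (−0.06 + 0.96)/2 = 0.45, so the main-effects model returns the mean of the two visit effects. The departure from 0.5 is simulation error shared by both fits.

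**Step 3: power when the effect exists only at Day 56.** The signal-to-noise ratio relative to a Day 56 contrast is

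[(d/2) / √(s²(1 + rho)/n)] ÷ [d / √(2s²/n)] = 0.5 × √(2/(1 + rho)).

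At 80% power the Day 56 contrast has non-centrality 1.645 + 0.842 = 2.486 to rounding (one-sided 5%), or 1.960 + 0.842 = 2.802 (two-sided 5%). Power is Φ(ratio × non-centrality − critical value).

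| rho | Ratio | One-sided 5% | Two-sided 5% |
|---|---|---|---|
| 0 | 0.707 | Φ(1.758 − 1.645) = 55% | 51% |
| 0.5 | 0.577 | Φ(1.435 − 1.645) = 42% | 37% |
| 0.8 | 0.527 | Φ(1.310 − 1.645) = 37% | 31% |

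**Step 4: power when the effect is equal at both visits.** The ratio becomes √(2/(1 + rho)), which is never below 1. One-sided power of the averaged test is then 93%, 89%, 85% and 82% at rho of 0.3, 0.5, 0.7 and 0.9, against 80% for a single-visit contrast.

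**The case against.** The strongest reply is that Section 11.3 names the factors of a repeated measures ANOVA and does not say main effects only. Protocols often leave the interaction unwritten, the surrounding text defines change visit by visit, and a statistical analysis plan that is not shown may include the term. This stands in part. The protocol does not exclude an interaction, and it would be wrong to infer that the trial cannot produce by-visit comparisons: the data for them are collected. But the section does list its fixed effects, the list does not yield the two differences in Section 5, and no by-visit comparison of arms appears anywhere else.

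It is also fair that the power loss belongs to one scenario. The product is taken from Day 0 and the primary outcome includes an increase at Day 28, so the protocol does not assume a zero effect there. Step 4 shows the opposite case, where averaging helps.

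Two stronger readings are tempting, and the documents do not support them:

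- A reader might infer from Section 4 that the two periods must be compared with each other, so that a Day 56 minus Day 28 contrast is missing. The sentence can equally mean product versus placebo within each period, and Section 5 defines change from baseline only.
- A reader might infer that covariates were promised and left out, because participant information "will be collected to account for inter-individual variability on study outcomes". That sentence commits to collection, not to model terms, and its list does not include age or sex.

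**Conclusion.** The point holds for the model as written. Section 11.3 returns one averaged difference for each product against placebo, whereas Section 5 defines the primary outcome at Day 28 and at Day 56 and Section 4 describes pre- and post-vaccination comparisons.

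The averaging follows from the model form alone. Equal weighting is exact only with complete data; participants who contribute Day 28 but not Day 56 move the weight towards the pre-vaccine visit.

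The fall from 80% power to between 37% and 55% (one-sided) depends on the assumed correlations, equal SDs at the two visits and a zero effect at Day 28. It illustrates the risk and does not predict the trial's power. With a constant effect there is no bias and no loss.

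**What to change.** In Section 11.3, add the group-by-visit interaction to the mixed model and pre-specify the contrast of each product with placebo at Day 28 and at Day 56. Carry the same wording into the statistical analysis plan.

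The cost is a change of wording, a few model degrees of freedom, and lower power than the averaged test if the effect is in fact constant across visits. No new data are needed.

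A Day 56 minus Day 28 contrast, a baseline-by-visit term, an unstructured covariance and age or sex covariates are optional choices. They are not needed to correct this error.

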# 8.9 Directions for Quadrivalent Influenza Vaccine

The QIV will be kept under proper storage with refrigeration kept between 2 to 8°C. The QIV will be administered via intramuscular injection using proper techniques and sanitation, preferably in the deltoid muscle of the upper arm, on Day 28.

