#### 11 STATISTICAL EVALUTION

#### 11.1 Determination of Sample Size

The planned total sample size will be 75 with 25 participants randomized to each study group. This sample size will enable detection of a difference in CD3+ of 10.8%, difference in CD4+ of 6.5%, difference in CD8+ of 4.9%, difference in CD45+ of 16.7% and difference in NK cells (CD56+) of 4.4% for lymphocytes; difference in IgA of 67 mg/dL (0.67 g/L), difference in IgG of 440 mg/dL (4.4 g/L), and difference in IgM of 133 mg/dL (1.33 g/L) for and immunoglobulins among the three arms at an overall 5% significance level and 80% power. This sample size takes into account a loss to follow up rate of 20%. The calculation is based on the studies by Olivares et al (19, 36, 37).

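### LOCF, allowed in Section 11.3, would enter a pre-vaccination Day 28 value as the post-vaccination Day 56 result, and the wording does not settle whether LOCF belongs to the main ITT analysis

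*Protocol*

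**What the plan says.** Protocol Section 11.3 states that missing primary and secondary endpoints "will be imputed with last-observation-carried-forward (LOCF) method or multiple imputation as a sensitivity analysis for ITT Population". The same section analyses changes by "repeated measures mixed model ANOVA, with study group and visit as the fixed effects", with the baseline value as a covariate, and adds: "All tests of significance for primary outcomes will be performed at one-sided", at alpha 0.05.

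The primary outcome in Section 5 is the increase in lymphocyte populations and immunoglobulins "in blood from baseline at Day 28 and 56"; these are the only two post-baseline measurements. Section 8.9 has the vaccine given "preferably in the deltoid muscle of the upper arm, on Day 28". In the Day 28 visit list (Section 9.6), blood collection is item 5 and vaccination is item 8. Section 4 says that the increases with the products and placebo "will be compared in the 28-day pre- and post-vaccination periods to examine the immune boosting effects of the products".

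On missing data, Section 11.1 states: "This sample size takes into account a loss to follow up rate of 20" per cent. It does not divide that loss by arm, or into before and after Day 28.

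**The concern.** The vaccination lies between the value that LOCF carries and the value that it replaces. Carrying Day 28 to Day 56 assumes that the immune challenge on which the design rests did nothing in that participant. All three arms are vaccinated, so any rise after Day 28 that is due to the vaccine is common to them. If more participants in one arm have Day 28 as their last value, LOCF removes more of the common rise from that arm and leaves a difference that is not a product effect. If the shares are equal, LOCF creates no false difference but dilutes a true post-vaccination one.

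Unequal loss is possible under the protocol's own rules. Section 9.7 removes participants who report COVID-19 after vaccination, while Section 5 makes confirmed COVID-19 infections a between-arm outcome. The sentence in Section 11.3 also names two methods with different assumptions and does not say which applies.

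**Working it through.** **The plan's own figure.** With 20% loss, 25 per arm leaves 25 × 0.80 = 20 evaluable per arm, so the enrolment and dropout figures agree. The detectable differences in Section 11.1 cannot be reproduced because no SDs are given. Nothing below depends on them.

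**Who is affected.** Section 11.2 keeps in the ITT population anyone who took product or placebo and has some effectiveness information after randomization. A participant with a Day 28 value and no later value is therefore in the ITT population and would be imputed. Under LOCF the Day 28-to-56 change is Day 28 minus Day 28 = 0.

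**Bias.** Let d be the share of an arm whose last value is Day 28, μ the mean at Day 28, and R the mean Day 28-to-56 response. Assume that dropout is unrelated to the values.

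- Mean Day 56 value after LOCF: d × μ + (1 − d)(μ + R) = μ + (1 − d)R.
- Active minus placebo, with no product effect: (d_placebo − d_active) × R.

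**Illustration.** Neither R, the SDs nor dropout by arm is in the protocol. Assumed: 25 per arm, d = 10% active and 30% placebo, correlation between visits 0.6. The bias at R = 0.5, 1.0 and 1.5 SD is (0.30 − 0.10) × R = 0.10, 0.20 and 0.30 SD. Simulated one-sided error at nominal 5%:

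| R (SD) | Bias, Day 56 contrast | Error, Day 56 contrast | Bias, average of both visits | Error, average of both visits |
|---|---|---|---|---|
| 0 | 0 | 5% | 0 | not run |
| 0.5 | 0.10 | 10–11% | 0.05 | 8% |
| 1.0 | 0.20 | 17–20% | 0.10 | 12–13% |
| 1.5 | 0.30 | 23–28% | 0.15 | 16–17% |

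The ranges for the Day 56 contrast cover an unadjusted t test (lower end) and baseline-adjusted analyses (8,000 to 20,000 runs per setting). The last two columns take the model in Section 11.3 literally, with group and visit but no interaction. The group effect then averages Day 28 and Day 56, and the bias halves.

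**Other settings.**

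- Imbalance reversed (30% active, 10% placebo, R = 1 SD): bias −0.20 SD, one-sided error about 0.7%.
- Equal 20% dropout, no product effect: bias about 0, error 5.1–5.3%.
- Equal 20% dropout and a true difference of 0.786 SD arising only after vaccination: expected 0.80 × 0.786 = 0.63 SD, which the simulation confirms. One-sided power is 0.72 (R = 1 SD) or 0.78 (R = 0.5 SD), against 0.96 with complete data. Part of that loss would follow from missing data under any method.

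**The case against.** The strongest reply is that the sentence ends by naming a sensitivity analysis, and that phrase can govern both methods. The main analysis would then be the mixed model on observed data, and LOCF could not touch the primary type I error. This reading is natural and cannot be excluded. The other reading, in which LOCF fills the ITT data and only multiple imputation is the sensitivity analysis, is also open. Choosing between sensitivity methods is commonly left to an SAP; the objection here is to a method that the protocol itself names and that does not fit its schedule.

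A reader might infer that every dropout after Day 28 gets a zero response. The documents do not support that. Section 7.5 (Removal by Qualified Investigator) asks for the end-of-study evaluations at withdrawal where possible, and Section 10.2.2 keeps some participants who stop product on all remaining visits. Those with a post-vaccination value are not affected.

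A reader might also infer that everyone lost before Day 28 has Day 0 carried forward. Under the ITT definition this reaches only those with some other effectiveness data after randomization, such as returned symptom questionnaires.

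The sizes are also open to challenge, and this stands. The 10%/30% split has no basis in the protocol. It is about 2–3 against 7–8 of 25, and its average of 20% uses up the whole planned loss after Day 28, although Section 9.5 removes COVID-19 and flu cases before then. The primary endpoints are total immunoglobulins and lymphocyte populations; strain-specific titers are left for future analysis. The rise in these totals may be small. With the group effect averaged over both visits, the error is about 6% at R = 0.2 SD with the 10%/30% split, and about 6% at R = 0.5 SD with a 15%/25% split.

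**Conclusion.** The mechanism holds on the protocol's own schedule. For an ITT participant whose last value is Day 28, LOCF enters a pre-vaccination value as the post-vaccination result. The bias under no product effect is the arm difference in such participants times R. It vanishes if either factor is zero, and its direction depends on which arm loses more. The error rates in the table show what could happen under stated assumptions; they are not a forecast for this trial.

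The documents do not establish that the primary type I error will be inflated, because LOCF may be confined to a sensitivity analysis. In that case the harm is smaller: the sensitivity analysis rests on the assumption of no response after vaccination and says little about how robust the main result is. Severity: should-fix, rising to must-fix only if LOCF is intended for the main ITT analysis.

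**What to change.** Replace the missing-data sentence in Section 11.3 so that it:

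1. deletes LOCF;
2. states that the main ITT analysis is the mixed model on all observed visits, without imputation. This uses participants with incomplete data and removes the LOCF bias if data are missing at random and the model is correct;
3. names one sensitivity approach: multiple imputation by arm that models the visit effect, with a delta-adjusted or placebo-based variant to test departures from missing at random.

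The cost is a rewrite of one sentence. No extra visits, samples or participants are needed.
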